We recently completed the first RCT of **Dutasteride for the reduction of heavy** drinking in men. Results support further examination of dutasteride as a treatment option for AUD. In total 189 treatment seeking men were enrolled of which 24 were screen failures and 23 failed to return for the baseline visit leaving 142 subjects randomized to medication (dutasteride n=74). Seven subjects did not return after the baseline randomization visit providing a modified intention to treat sample of 135 subjects (68 dutasteride and 67 placebo) who provided drinking data post-randomization. One hundred seven subjects completed the entire 12-week treatment. The mean number of treatment weeks completed were not different between arms (dut 10.2 vs. pbo 10.7). 3α androstanediol glucuronide levels were decreased by 80% in the dutasteride group at both 6 and 12 weeks vs. 0% in pbo treated subjects confirming the anticipated pharmacological effect for our study design. There were no significant differences between groups (dutasteride vs. pbo) for measures of alcohol consumption during the 60-days prior to screening including the number of standard drinks (SD) per week (48.8 vs. 47.3), number of heavy drinking days (HDD, 5 or more drinks for men) per week (5.2 vs. 5.2), or abstinent days per week (0.67 vs. 0.62). While the dutasteride group were more likely to have had a prior episode of treatment for alcohol use (59% vs. 40%, p=0.03) the number of DSM-IV AD criteria did not significantly differ between groups (4.3 vs. 4.0).

[figure not shown]
Safety. There were no study related serious adverse effects. The proportion of subjects exposed to study medication who reported at least one non-serious adverse

[figure not shown]
effect was not significantly different for the dutasteride vs. pbo groups 71.6% vs. 67.1% similarly, the number of side effects per subject was not different between dutasteride and placebo groups, 1.36 ± 1.46 vs. 1.03 ± 1.10 . Adverse events that were reported by more patients in the dutasteride compared with the placebo arm included stomach discomfort (16.4% vs. 4.5%, p=0.04) and reduced libido (9.0% vs. 0%; p=0.03). More subjects in the dutasteride arm (n=4) than the pbo arm (n=1) stopped medication due to side effects. Beck Depression Inventory scores were low in both treatment arms at baseline (10.4 dut vs. 7.5 pbo) and reduced to a similar degree during the 12-week treatment (-3.3 dut vs. -2.4 pbo, t=0.6; p=0.5).

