Drinking outcomes. Comparison of treatment groups for the modified intention to treat sample (N=135) on the primary outcomes of HDD/week and drinks/ week using generalized linear mixed models (GLMM) showed significant treatment x time interactions (HDD F=9.2; df=1,1406, p=0.002 and SD/wk F=4.8, df=1,1406, p= 0.028). While a minority of our subjects smoke, in view of prior reports of differential medication effects among smokers vs. non-smokers for naltrexone we examined GLMM models that included smoking status, treatment condition, treatment x time, and treatment x smoking as predictors, and identified significant 2-way interactions of treatment x time (F=9.1, df=1,1404, p=0.003 and F=4.4, df=1,1403, p=0.035 for HDD and SD/wk, respectively), and treatment x smoking (F=8.4, df=1,1404, p=0.004 and F=10.9, df=1,1403, p=0.001 for HDD and SD/wk, respectively), such that smokers (n=12) treated with dutasteride drank more throughout the treatment period than smokers treated with pbo (n=12), while the opposite response was observed for non-smokers (dutasteride=56; pbo=55). Smokers and nonsmokers did not differ on baseline drinking, age, Spielberger State Anxiety (SAI) or Beck Depression Inventory (BDI) scores. The interaction of drug x smoking status may relate to the induction by tobacco of phase I metabolism cytochrome P450 and aldo-keto reductase enzymes (Nagaraj, Beckers et al. 2006), the latter of which are involved in neuroactive steroid biosynthesis and metabolism. A prior study showed a positive correlation between serum cotinine levels and the neuroactive steroid allopregnanolone in a sample of 28 men (Marx, Trost et al. 2006). Somewhat surprisingly, with limited exceptions (Fucito, Park et al. 2012, Litten, Ryan et al. 2013, Schacht, Randall et al. 2017) reports for recent RCTs for AUD either did not report the proportion of smokers (Johnson, Ait-Daoud et al. 2003, Johnson, Rosenthal et al. 2007, Johnson, Ait-Daoud et al. 2011, Johnson, Seneviratne et al. 2013, Kranzler, [name] et al. 2014) or did not include smoking status in the analysis of outcomes (Anton, O'Malley et al. 2006, Anton, Myrick et al. 2011, Fertig, Ryan et al. 2012, Litten, Fertig et al. 2012). Interestingly, in the reports by Fucito et al. (Fucito, Park et al. 2012) and Schacht et al. (Schacht, Randall et al. 2017) naltrexone only benefited drinkers who also smoked while our results with dutasteride indicated only non-smokers were responsive, presumably reflecting distinct mechanisms of change. We will include smokers in the proposed study to further evaluate our initial findings. Dutasteride nonresponsive smokers in phase 1 may experience treatment responsive to naltrexone in phase 2 of the proposed study which would support use of smoking as a factor in individualized treatment recommendations.

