
For the majority non-smoker group (n=111) there was a significant interaction of medication group by treatment week (HDD/wk F=6.2, df=1,1183, p=0.013; and SD/wk F=4.7, df=1,1183, p=0.031) **Figure 1**, such that dutasteride treated subjects reduced drinking over time more than placebo subjects. During the last 4 weeks of the 12-week treatment period, the proportion of subjects with a \geq 60% reduction in SD/wk compared with screening (which represents a clinically meaningful reduction from a group average of 48 SDs/wk to less than 20) was significantly greater for the dutasteride vs. the pbo group [49% vs. 20%; χ^2 =8.3, p=0.004; OR=3.8 (95% Cl=1.5-9.8)]. Additionally, among the 91 per protocol completers, during the last month of treatment 33% of subjects in the dutasteride arm had no heavy drinking and 27% no hazardous drinking (no HDDs and no more than 14 SD/wk) compared with 11% and 2% of pbo- treated subjects respectively [no HDD days [χ^2 =6.7, p=0.01; OR = 4.1, NNT=5]; and no hazardous drinking [χ^2 =11.1, p=0.001; OR = 16.4, NNT=4]. The additional analysis described below focuses on the group of 111 non-smokers.

[figure not shown]
Figure 1. Heavy Drinking Days per week (left) and Standard Drinks per week (right) for pbo vs dutasteride treated nonsmokers (mean±SEM).

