2.C.9.a.2. Efficacy: Primary treatment outcomes will be defined in terms of HDD/wk and SD/wk based on TLFB reports of drinking. Reduction in these measures is related to health benefits of reduced drinking. These are the measures that are used to define non-hazardous drinking. Secondary outcomes will include proportion of days abstinent (PDA), % of subjects with no HDDs, % of subjects with non-hazardous drinking (no HDD and SD/week <15 men/<8 women) during the last 4 weeks of each treatment phase, and change in PEth at end of each treatment phase relative to baseline.

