For the phase 1 comparison of dutasteride and pbo over time, efficacy analyses will be performed using generalized linear mixed (GLMM) models implemented in SPSS. GLMM incorporates within subject correlation effects important in examination of repeated measures, can incorporate multiple covariates, interactions, random and fixed effects, nonnormal distributions, and is often recommended for designs such as proposed (Mallinckrodt C 2017). Medication group will be treated as a factor and treatment week as a continuous covariate. Sex, smoking status, treatment goal (stop vs. reduce drinking), and use of concurrent medication for co-morbid psychiatric conditions will also be examined as baseline between-subject covariates. Medication group, week, and the other covariates will be modeled as fixed effects, and the intercept will be modeled as random effects. For the outcome HDD/wk a binomial distribution with logit link will be used where the number of HDD during the week will be the numerator and number of observed days the denominator. For the outcome SD/wk a negative binomial distribution with log link will be used. An interaction term between medication group and the week term(s) will be used to evaluate whether the efficacy of dutasteride compared to pbo in reducing drinking varies over time. Interaction effects of sex and treatment condition will also be examined. Pretreatment drinking will be controlled using baseline TLFB drinking data as a covariate. The robustness of results will be evaluated by running the model under three different conditions: 1) modified intention to treat using all available outcome information from subjects with at least 1 post-randomization visit, 2) data from 12-week per protocol completers, and 3) multiple imputation using 10 imputed data sets with weekly drinking and baseline covariates thought predictive of the outcomes or missingness included in the imputation phase.

For aim 2, phase 2 outcomes, the within-subjects analysis will compare drinking during phase 1 against phase 2 for three groups: a) patients responsive to dutasteride in phase 1 and continuing on dutasteride for an additional 12-weeks in phase 2, to examine whether the response is maintained with continued treatment; b) phase 1 non-responders crossed over from pbo in phase 1 to dutasteride in phase 2 to provide a second contrast using an A-B design of the efficacy of dutasteride compared with pbo; and c) phase 1

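### The phase 1 model has only a random intercept and no stated standard-error method, so its medication-by-week test is too liberal if slopes vary, weeks are serially correlated or HDD counts are overdispersed

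*Combined protocol and SAP*

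**What the plan says.** Section 2.C.9.a.2 (Efficacy) sets the two primary outcomes: "Primary treatment outcomes will be defined in terms of HDD/wk and SD/wk based on TLFB reports of drinking". The phase 1 comparison uses generalized linear mixed models with week as a continuous covariate. On the random part the plan says: "Medication group, week, and the other covariates will be modeled as fixed effects, and the intercept will be modeled as random effects". On the distribution: "For the outcome HDD/wk a binomial distribution with logit link will be used", the denominator being the days observed that week. SD/wk is negative binomial with a log link.

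On the test at issue: "An interaction term between medication group and the week term(s) will be used to evaluate whether the efficacy of dutasteride compared to pbo" changes over time. On robustness: "The robustness of results will be evaluated by running the model under three different conditions". These conditions are all available data (modified intention to treat), 12-week completers, and multiple imputation.

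The section notes in general terms that mixed models account for within-person correlation. Beyond the random intercept it selects no structure. It gives no random week slope, residual covariance, binomial overdispersion term or standard-error method. Robust errors are neither chosen nor ruled out.

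Section 2.B.2 (Preliminary studies) reports that the earlier trial's primary comparison "showed significant treatment x time interactions (HDD F=9.2; df=1,1406, p=0.002 and SD/wk F=4.8, df=1,1406". Among non-smokers it reads the same kind of interaction as benefit: "such that dutasteride treated subjects reduced drinking over time more than placebo subjects".

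**The concern.** With a random intercept alone, a person's 12 weeks are treated as independent once that person's average level is known, and weekly HDD counts as no more variable than a binomial allows. The model-based standard error of the slope difference is then too small if any of three features is present:

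- (a) people change at different rates;
- (b) a person's neighbouring weeks are more alike than distant ones;
- (c) for HDD/wk only, weekly counts are overdispersed. The negative binomial for SD/wk has its own dispersion parameter.

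None of the three robustness conditions would reveal this, because each refits the same covariance model to different data. The stake is a false claim that the arms diverge over time, which could be reported as efficacy. Section 2.C.9.a.2 names no other term as the deciding one.

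**Working it through.** **Inputs from the documents.** 190 randomized 1:1, 160 expected to complete phase 1, 12 weeks (sections 2.C.2, 2.C.3.d and 2.C.9.b). Binomial of up to 7 days for HDD/wk, negative binomial for SD/wk, random intercept, medication-by-week. The plan gives no error rate for this test, so there is no plan figure to reproduce.

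**Inputs that are assumptions.** All intercept, slope and noise SDs and all serial correlations.

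**Hand check of the mechanism (HDD/wk, feature a).** For weeks 1-12 the sum of squares of week about its mean is (12³ − 12)/12 = 143. If everyone averages 3.5 HDD/wk, each week carries information 7 × 0.5 × 0.5 = 1.75 on the logit scale. One person's slope then has sampling variance of about 1/(1.75 × 143) = 0.0040. True slope variance τ² adds to this, but the model-based error omits it:

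- true SE / model SE = √(1 + τ²/0.0040)
- τ = 0.05: √(1 + 0.0025/0.0040) = 1.27; false-positive rate 2Φ(−1.96/1.27) ≈ 12%
- τ = 0.10: √(1 + 0.0100/0.0040) = 1.87; rate 2Φ(−1.96/1.87) ≈ 29%

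This is a rough upper figure, because people away from 3.5 HDD/wk carry less information and their sampling variance is larger. The full simulations should come out somewhat lower, and they do.

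**Simulations with no true medication-by-week effect.**

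- A: 95 per arm, 30 people stopping at a random week, 1,000 runs per case; intercept SD 1.3 logit (HDD) or 0.6 log (SD/wk).
- B: 80 per arm, complete data, 2,000 runs per case; intercept SD 1.5 logit or 0.6 log.
- C: HDD/wk only, 190 people with 30 dropouts, 800 runs per case.

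The Monte Carlo standard error near 5% is √(0.05 × 0.95/runs): 0.7, 0.5 and 0.8 points. Near 25% it is 1.4, 1.0 and 1.5 points.

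Two-sided rejection at nominal 5%, model-based errors:

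| Case | A | B | C |
|---|---|---|---|
| HDD, none present | 3.7% | 4.4% | 5.2% |
| HDD, slope SD 0.05 logit/week | 8.9% | 10.6% | – |
| HDD, slope SD 0.10 | 24.0% | 23.3% | 27.3% |
| HDD, uncorrelated weekly noise SD 0.35 | 5.6% | – | – |
| HDD, uncorrelated weekly noise SD 0.7 | 10.5% | 11.1% | – |
| HDD, noise SD 0.7, AR(1) 0.3 / 0.5 / 0.6 | 14.5 / – / 19.5% | – / 16.8 / –% | – |
| SD/wk, none present | 4.6% | 5.2% | – |
| SD/wk, slope SD 0.02 / 0.03 / 0.04 log/week | 9.6 / – / 20.5% | – / 14.2 / –% | – |
| SD/wk, noise SD 0.35 log, AR(1) 0.3 / 0.5 / 0.6 / 0.7 | 11.9 / – / 19.5 / –% | – / 13.8 / – / 17.0% | – |

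Mild HDD overdispersion (noise SD 0.35, no serial correlation) cannot be told from nominal.

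**Same fits, participant-clustered robust errors.** A: 3.8-5.9%. B: 4.6-6.2%. C: 5.8% at slope SD 0.10.

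**Consistency.** In A, model SE divided by the true SD of the estimate was 0.85 at HDD slope SD 0.05 and 0.60 at 0.10. Then 2Φ(−1.96 × 0.85) = 9.6% and 2Φ(−1.96 × 0.60) = 24.0%, against 8.9% and 24.0% simulated. The excess rejections come from the standard error.

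**What is not affected.** In A the medication effect at mid-period rejected in 4.2-6.5% of runs.

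**Benchmark.** A result of F = 4.8 loses 5% significance once the true SE is √(4.8/3.84) = 1.12 times the reported one; F = 9.2 needs √(9.2/3.84) = 1.55 times. At HDD slope SD 0.05 the simulated factor was about 1.2 (1/0.85 in A, 1.19 in B). This shows how little is needed to move a moderate result. It does not show that the earlier trial's errors were wrong.

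**The case against.** The strongest reply is that this is an omission. If the analysts use robust errors, nothing is wrong, and no figure in the documents shows that any of the three features is present. That stands: the finding is conditional and every inflation percentage is assumed.

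Second, the interaction is described as testing whether efficacy varies over time. Aim 1 power rests on change from baseline to the last month, and section 2.C.9.a.2 also plans last-4-week proportions and PEth. That stands too, and it limits the consequence. It does not remove it, since no deciding term is named and section 2.B.2 shows how the interaction was read before.

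Three stronger readings are tempting, and the documents do not support them.

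- A reader might infer from the denominator df of 1406 that the earlier trial's errors were too small. Large df do not show how the errors were computed. Replacing 1406 by 133 moves the SD/wk p-value only from 0.029 to 0.030.
- A reader might infer from the Aim 2a margin (section 2.C.9.b) that within-person change exceeds what a random intercept allows. The section does not say which SD it used, and it concerns selected responders across both phases. The same sentence's 5 SDs/wk, if it rests on a change SD at two-sided 5%, gives 5 × √40/2.802 = 11.3. A random-intercept negative binomial yields that without slope variation or serial correlation: at mean 40 and dispersion 0.13, √(2 × (40 + 0.13 × 40²)/4) = 11.1 between two 4-week averages.
- A reader might infer that the whole phase 1 efficacy comparison is unsound. The mid-period result above says otherwise.

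**Conclusion.** The concern holds in conditional form. As written, the model protects the medication-by-week test only if slopes do not vary, weeks are not serially correlated and HDD counts are not materially overdispersed. If model-based errors are used and one of these fails, false positives exceed 5%. The range runs from a rate indistinguishable from nominal with mild overdispersion to about a quarter of null trials at an HDD slope SD of 0.10 logit/week. About half of the false positives would favour dutasteride. The direction agrees across separate simulations; the size in this trial is unknown. It matters to the extent that the interaction is again read as benefit. It is worth settling before analysis, because the stated covariance has a better and cheap alternative, and silence leaves the error method open to choice after the results are seen.

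**What to change.** Add one sentence to section 2.C.9.a.2: in both primary models (HDD/wk and SD/wk), tests and confidence intervals for fixed effects use robust covariances clustered on participant. A random week slope may be listed as a sensitivity analysis. It targets varying slopes directly, but it is not a general remedy for serial correlation or overdispersion.

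The cost is one sentence and one model setting. The interval for the slope difference was about 1.1-1.7 times as wide in simulated cases where a feature was present, and essentially unchanged (1.00) where none was.
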